7.3 Expedited Adverse Event Reporting

7.3.1 Expedited AE reporting for this study must use CTEP-AERS (Adverse Event Reporting System), accessed via the CTEP Web site (http://ctep.cancer.gov). The reporting procedures to be followed are presented in the "NCI Guidelines for Investigators: Adverse Event Reporting Requirements for DCTD (CTEP and CIP) and DCP INDs and IDEs" which can be downloaded from the CTEP Web site (http://ctep.cancer.gov). These requirements are briefly outlined in the tables below (section 7.3.3).

In the rare occurrence when Internet connectivity is lost, a 24-hour notification is to be

made to CTEP by telephone at [contact]. Once Internet connectivity is restored, the 24-hour notification phoned in must be entered electronically into CTEP-AERS by the original submitter at the site. Also, if internet connectivity is not re-established within 24 hours, notify the following by telephone and or email.

PBTC-033 Study Chair:

[name]. Pediatric Hematology-Oncology Texas Children's Cancer Center Baylor College of Medicine [name] [contact] [contact] Email: [contact]

PBTC OBC:

[name], MSHS, BSMT St. Jude Children's Research Hospital Department of Biostatistics [contact] [contact] or [name] Email: [contact]

7.3.2 CTEP-AERS is programmed for automatic electronic distribution of reports to the following individuals: Study Coordinator of the Lead Organization, Principal Investigator, and the local treating physician. CTEP-AERS provides a copy feature for other e-mail recipients.

7.3.3 Expedited Reporting Guidelines

Use the NCI protocol number and the protocol-specific patient ID assigned during trial registration on all reports.

Note: A death on study requires both routine and expedited reporting regardless of causality, unless as noted below. Attribution to treatment or other cause must be provided.

Death due to progressive disease should be reported as **Grade 5 "Neoplasms benign**, **malignant and unspecified (incl cysts and polyps) - Other (Progressive Disease)"** under the system organ class (SOC) of the same name. Evidence that the death was a manifestation of underlying disease (*e.g.*, radiological changes suggesting tumor growth or progression: clinical deterioration associated with a disease process) should be submitted.

Phase 1 and Early Phase 2 Studies: Expedited Reporting Requirements for Adverse Events that Occur on Studies under an IND/IDE within 30 Days of the Last Administration of the Investigational Agent/Intervention ^{1, 2}

FDA REPORTING REQUIREMENTS FOR SERIOUS ADVERSE EVENTS (21 CFR Part 312)
NOTE: Investigators MUST immediately report to the sponsor (NCI) ANY Serious Adverse Events, whether or not they are considered related to the investigational agent(s)/intervention (21 CFR 312.64)
An adverse event is considered serious if it results in ANY of the following outcomes:

Death
A life-threatening adverse event
An adverse event that results in inpatient hospitalization or prolongation of existing hospitalization for ≥ 24 hours
A persistent or significant incapacity or substantial disruption of the ability to conduct normal life functions
A congenital anomaly/birth defect.

6) Important Medical Events (IME) that may not result in death, be life threatening, or require hospitalization may be considered serious when, based upon medical judgment, they may jeopardize the patient or

definition. (FI ALL SERIOUS advers	hay require medical or surgical intervention to prevent one of the ou DA, 21 CFR 312.32; ICH E2A and ICH E6). The events that meet the above criteria MUST be immediately reported trames detailed in the table below.	
Hospitalization	Grade 1 and Grade 2 Timeframes	Grade 3-5 Timeframes
Resulting in Hospitalization ≥ 24 hrs	lospitalization 10 Calendar Days ≥ 24 hrs	
Not resulting in Hospitalization ≥ 24 hrs	Not required	Days
	owed by a complete expedited report within 5 calendar days of the Days" - A complete expedited report on the AE must be submitted to AE.	
 "10 Calendar learning of th ¹Serious adverse ever agent/intervention and Expedited 24-hour no 	Days" - A complete expedited report on the AE must be submitted	within 10 calendar days of stigational ng as follows:
Expedited 10 calenda		
	F or SPECT IND agents, the AE reporting period is limited to 10 rad arest whole day, after the agent/intervention was last administered. ting period.	
Effective Date: May 5	, 2011	

7.4 Routine Adverse Event Reporting

All Adverse Events must be reported in routine study data submissions. AEs reported through CTEP-AERS must also be reported in routine study data submissions.

7.5 Secondary Malignancy

A *secondary malignancy* is a cancer caused by treatment for a previous malignancy (*e.g.*, treatment with investigational agent/intervention, radiation or chemotherapy). A secondary malignancy is not considered a metastasis of the initial neoplasm.

CTEP requires all secondary malignancies that occur following treatment with an agent under an NCI IND/IDE be reported via CTEP-AERS. Three options are available to describe the event:

- Leukemia secondary to oncology chemotherapy (*e.g.*, acute myelocytic leukemia 45)
- Myelodysplastic syndrome (MDS)
- Treatment-related secondary malignancy

Any malignancy possibly related to cancer treatment (including AML/MDS) should also be reported via the routine reporting mechanisms outlined in each protocol.

7.6 Second Malignancy

A second malignancy is one unrelated to the treatment of a prior malignancy (and is **NOT** a metastasis from the initial malignancy). Second malignancies require **ONLY** routine reporting via CDUS unless otherwise specified.

8. PHARMACEUTICAL INFORMATION

A list of the adverse events and potential risks associated with the investigational or commercial agent administered in this study can be found in section 7.1.

8.1 ABT-888 (NSC # 737664)

Chemical Name: 1*H*-Benzimidazole-7-carboxamide, 2-[(2*R*)-2-methyl-2-pyrrolidinyl]-Other Names: Veliparib, A-861695.0 Classification: Poly (ADP-ribosome) polymerase (PARP) Inhibitor CAS Registry Number: 912444-00-9 Molecular Formula: $C_{13}H_{16}N_4O$ M.W.: 244.29

Mode of Action: ABT-888 is a potent oral PARP1/2 inhibitor whose pharmacological properties include high solubility (crosses the blood brain barrier), linear PK, and low potential drug-drug interactions. In vivo and in vitro, ABT-888 inhibits the formation of poly (ADP-ribose) (PAR) polymer and prevents the repair of DNA that is damaged by cytotoxic agents. Furthermore, ABT-888 can increase antitumor efficacy of temozolomide, cisplatin, carboplatin, cyclophosphamide, irinotecan, or radiation therapy.

[figure not shown]
Route of Administration: The oral solution can be administered with water or juice if needed. ABT-888 will be administered twice daily (~12 hours apart), Monday through Friday, during radiation therapy. The morning dose of ABT-888 should ideally be given 60-120 minutes prior to daily irradiation. For children who require sedation for irradiation and must remain NPO in the morning, ABT-888 may be given each night prior to bedtime, and the morning dose should be given shortly after the child recovers from sedation, adhering as closely to an every-12-hour schedule as possible. However, if permitted by the local sedation/anesthesia guidelines, ABT-888 may be given each morning prior to sedation, ideally 60-120 minutes prior to irradiation. See additional administration instructions in section 5.1. See **Appendix** D for calculated dose of ABT-888 capsules for patients taking capsules only.

[figure not shown]
During the maintenance therapy (starting on week 11 of protocol therapy), ABT-888 will be given twice daily (~12 hours apart), on days 1-5 of each 28-day course, with the morning dose of ABT-888 to be given 60-120 minutes prior to the morning temozolomide dose. The capsules should be swallowed whole without breakage. See Appendix E for the calculated dose for the ABT-888 capsules during maintenance for patients taking capsules only. ABT-888 capsules or the oral solution may be administered without regard to meals. If emesis occurs within 10 minutes of administration, the dose should be repeated.

Potential Drug Interactions: Clinical studies evaluating the metabolism of ABT-888 have not been conducted. However, results from the in vitro analysis reveal that this agent is metabolized by multiple isoenzymes – CYP1A1, 2D6, 2C19 and 3A4. ABT-888 is neither a potent inhibitor

nor a potent inducer of the CYP-450 isoenzymes. Use caution when concomitantly administer with drugs that are substrate, inhibitor, inducer of CYP1A1, 2D6, 2C19 and 3A4.

ABT-888 clears primarily in the urine as intact parent drug along with metabolites suggesting that renal function plays an important role in the drug clearance and its metabolites. Use caution when concomitantly administer with oxalipaltin, carboplatin, cisplatin, and topotecan in patients with pre-existing renal impairment.

Availability: *ABT-888* in both capsule and oral solution formulations are provided to the NCI under a Collaborative Agreement between the Pharmaceutical Collaborator and the DCTD, NCI (see section 12.3).

8.1.2 Agent Ordering and Agent Accountability

NCI supplied agents may be requested by the Principal Investigator (or their authorized designee) at each participating institution. Pharmaceutical Management Branch (PMB) policy requires that agent be shipped directly to the institution where the patient is to be treated. PMB does not permit the transfer of agents between institutions (unless prior approval from PMB is obtained.) The CTEP assigned protocol number must be used for ordering all CTEP supplied investigational agents. The responsible investigator at each participating institution must be registered with CTEP, DCTD through an annual submission of FDA form 1572 (Statement of Investigator), Curriculum Vitae, Supplemental Investigator Data Form (IDF), and Financial Disclosure Form (FDF). If there are several participating investigators at one institution, CTEP supplied investigator at that institution.

Active CTEP-registered investigators and investigator-designated shipping designees and ordering designees can submit agent requests through the PMB Online Agent Order Processing (OAOP) application https://eapps-ctep.nci.nih.gov/OAOP/pages/login.jspx. Access to OAOP requires the establishment of a CTEP Identity and Access Management (IAM) account https://eapps-ctep.nci.nih.gov/iam/ and the maintenance of an "active" account status and a "current" password. For questions about drug orders, transfers, returns, or accountability, call [name] Monday through Friday between 8:30 am and 4:30 pm (ET) or email PMB after [contact] anytime.

For the radiation phase of the protocol treatment, for patients taking capsules only, please order sufficient number of capsules for 30 days of treatment. For patients receiving the oral solution drug must be ordered and dispensed monthly during radiation.

Agent Inventory Records

The investigator, or a responsible party designated by the investigator, must maintain a careful record of the inventory and disposition of all agents received from DCTD using the NCI Drug Accountability Record Form (DARF). (See the NCI Investigator's Handbook for Procedures for Drug Accountability and Storage.)

8.2 Temozolomide (Temodar[™]; NSC#: 362856)

Sites should refer to the FDA approved package insert for additional information on the commercial drug.

Formulation:

Temozolomide is available in 5 mg, 20 mg, 100 mg, 140 mg, 180 mg and 250 mg capsules.

Stability & Storage: Capsules should be stored at 25°C (77°F); excursions permitted to 15-30°C (59-86°F). The commercial product has an expiration date on the bottle.

Procedure for Proper Handling and Disposal

Chemotherapy precautions should be utilized in preparation.

Route/Frequency of Administration: Dose should be rounded to the nearest 5 mg. See Appendix E for dosing determination. Temozolomide should be administered 60-120 minutes after the morning ABT-888 dose. If a patient has emesis within 10 minutes of receiving a dose, the dose should be repeated.

For patients unable to swallow intact capsules, capsules may be opened and mixed with apple juice or applesauce immediately prior to administration. If opening of capsules is necessary, it should be performed by hospital staff trained in handling chemotherapeutics whenever possible. However, if necessary, adult family members are allowed to open the temozolomide capsules at home, provided that they follow the instructions in Appendix C strictly, as well any additional instructions given by hospital pharmacists trained in handling chemotherapeutics.

Agent Ordering

Temozolomide is available from commercial sources by the treating hospital pharmacy.

9. CORRELATIVE AND SPECIAL STUDIES

9.1 Laboratory Correlative Studies

9.1.1 Plasma Pharmacokinetics Studies

Participation in the pharmacokinetic studies is required during the Phase I portion of the study and strongly encouraged but optional during Phase II. Plasma pharmacokinetics samples will be obtained on days 1 (first dose) and 4 (steady state) during the first week of ABT-888 and

radiation treatment. If day 4 falls on a Saturday, please collect steady state PK samples on day 3. If day 4 falls on a Sunday, please collect steady state PK samples on day 5.

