2.2.3.2 Pharmacology/Pharmacokinetics/Correlative Biological Studies

Pharmacokinetic data from children enrolled onto PBTC-027 (Table 2) showed that, based on $AUC_{0->12hr}$ and steady state C_{max} , pediatric ABT-888 drug exposure at 15 mg/m² is similar to adult dosing at 20 mg bid, and pediatric ABT-888 drug exposure at 20 mg/m² bid is slightly lower than adult dosing at 40 mg bid (AUC_{0->12hr} 1.55 µg•hr/mL in 1 child vs 1.87 +/- 0.49 µg•hr/mL in 3 adults). Based on maximally effective AUC_{0->24hr} of 3 µg•hr/mL predicted from animal models and observed AUC_{0->24hr} of 3.74 µg•hr/mL in adults receiving ABT-888 at 40 mg bid, it appears that pediatric dosing of 20 mg/m² bid or higher would be required to match the drug exposure seen in adults receiving 40 mg bid. Furthermore, PARP inhibition in PBMCs from children on PBTC-027 was highly variable, averaging only 31.5 +/- 33.6% inhibition in seven patients.

Table 2								
Pharm	Pharmacokinetic Data, PBTC-027 versus Adult Mean ± Standard Deviation							
	PBTC-027 PBTC-027 Adult Adult 20 mg/m ² 15 mg/m ² 40 mg bid 20 mg bid (22 mg/m ²) (11 mg/m ²)							
Number of patients	Number of patients1633							
AUC _{0->12hr} (μ g•hr/mL) 1.55 1.05 ± 0.42 1.87 ± 0.49 0.99 ± 0.37								
Steady State C _{max} (ng/ml)	379	222 ± 64	348 ± 55	171 ± 39				

Т	a	bl	ما	2
	а	U.	IV.	4

Based on the preliminary PK and pharmacodynamic data from PBTC-027, the trial was amended in an effort to optimize ABT-888 drug exposure and PARP inhibition. The revised treatment schema is as follows:

Revised Treatment Schema								
Dose Level	ABT-888 Dose, mg/m ² /dose BID	TMZ Dose, mg/m ² /dose daily x 5						
Dose Level	x 5 days	days						
0	15 mg/m ² /dose BID	135 mg/m ² /day						
1 (starting dose level)	20 mg/m ² /dose BID	135 mg/m ² /day						
2	25 mg/m ² /dose BID	135 mg/m ² /day						

Table 3

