9.1.1.1 Sampling Strategy for Pharmacokinetic Study

First dose pharmacokinetic study of ABT-888, Day 1 of ABT-888 and Radiation treatment Blood samples will be collected prior to the first dose of ABT-888 on day 1 of radiation treatment, and then at 0.5, 1, 2 and 6-8 hours after the first dose of ABT-888. Blood samples may be obtained either by repeated phlebotomies or through temporary or permanent intravenous catheters/devices. The pre-ABT-888 sample may be obtained at study entry, provided that the specimen is processed and stored appropriately per section 9.1.1.2.

For children who require sedation for radiation and are not able to take the p.o. medication due to local requirements for NPO prior to sedation, the pre-ABT-888 sample may be obtained at study entry or at any time prior to the first dose of ABT-888 (to be administered the night prior to first day of radiation treatment). Subsequent PK samples outlined above (at 0.5, 1, 2 and 6-8 hours after a dose of ABT-888) should be collected after the child awakens from sedation and after the second dose of ABT-888 is given on day 1 of radiation treatment.

Steady state pharmacokinetic study of ABT-888, Day 4 of ABT-888 and Radiation treatment Blood samples should be obtained prior to the A.M. ABT-888 dose on day 4 of radiation treatment, and then at 2 hours after the A.M. dose. Blood samples may be obtained either by repeated phlebotomies or through temporary or permanent intravenous catheters/devices.

For children who require sedation for radiation and must remain NPO in the morning, the day 4 samples should be obtained after the child awakens from sedation on day 4 and then at 2 hours after the day-4 ABT-888 dose has been given.

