9.1.1.2 Sampling Collection and Processing Instructions

Blood samples (a minimum of 2.5 ml for children < 12 kg, and 3-5 ml for children > 12 kg) should only be collected in potassium EDTA tubes, provided by AbbVie. All information about the PK kits and ordering instructions are available on the PBTC-033 members' website in the Protocol Specific Instructions/Forms section. Sites are to record the exact time that the sample is drawn along with the exact time that the study drug is administered on the PK Sample Transmittal form located in the PBTC-033 Protocol Specific Instructions/Forms section of the PBTC members' webpage.

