13.2.3 Statistical Analysis of Pharmacokinetics

Plasma drug concentrations and pharmacokinetic parameters will be presented in tabular and graphical form. Pharmacokinetic parameters of interest, such as apparent volume of the central compartment (Vc/F), elimination rate constant (Ke), half-life (t1/2), apparent oral clearance (CL/F), and area under the plasma concentration time curve (AUC) will be estimated using compartmental methods. Dose proportionality in pharmacokinetic parameters will be investigated by performing one-way analysis of variance (ANOVA) on dose-normalized parameters.

In addition to estimating individual pharmacokinetic parameters, we will also estimate the population parameters using nonlinear mixed effects modeling methods (NONMEM). This method estimates the population parameters and both the inter- and intra-subject variability. Once the population parameters and corresponding covariance matrix are estimated, individual estimates can be obtained using post hoc analysis.

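### For Thursday and Friday starters the 'steady state' PK samples fall on a Monday after an undosed weekend, so the pre-dose sample is a washout level and not a trough

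*Combined protocol and SAP*

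**What the plan says.** Section 8.1 gives the radiation-phase schedule: "ABT-888 will be administered twice daily (~12 hours apart), Monday through Friday, during radiation therapy". Section 5.1.1 says the same and starts the drug on the first day of radiation, without fixing a weekday. Thursday and Friday starts are therefore allowed.

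Section 9.1.1 sets the default sampling days: "Plasma pharmacokinetics samples will be obtained on days 1 (first dose) and 4 (steady state"). A Saturday day 4 moves back to day 3. For a Sunday, the rule is: "If day 4 falls on a Sunday, please collect steady state PK samples on day 5".

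Section 9.1.1.1 defines the steady-state visit as two samples, one before the morning dose and one 2 hours after it: "Blood samples should be obtained prior to the A.M. ABT-888 dose on day 4 of radiation treatment". For children who must fast for sedation, the same section describes the first dose as "to be administered the night prior to first day of radiation treatment".

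PK sampling is required in Phase I and optional in Phase II. PK during radiation is listed among the Phase I primary objectives in section 1.1.

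**The concern.** The weekend rules in 9.1.1 only make sense if day 4 is a calendar day, because the fourth treatment day would not normally fall on a weekend. The rules keep the visit off Saturday and Sunday but take no account of the dosing gap. A Monday visit in the first week follows two days without drug. The pre-dose sample is then what remains after washout, and the 2-hour sample in effect repeats the first-dose sample from day 1.

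The schedule is sparse. Day 1 sampling ends at 6-8 hours, and the steady-state visit has two samples. The pre-dose sample is the only one planned near the end of a 12-hour dosing interval. Anyone who takes the protocol's label at face value, in a trough summary, an accumulation ratio or a day 1 versus day 4 comparison, would mix true troughs with values near zero.

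**Working it through.** **Calendar.** Assumed dose times are 08:00 and 20:00, Monday to Friday, with the 9.1.1 rules applied as written:

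| Start | Sampling day | Prior doses | Hours since last dose |
|---|---|---|---|
| Monday | Thursday, day 4 | 6 | 12 |
| Tuesday | Friday, day 4 | 6 | 12 |
| Wednesday | Friday, day 3 (Saturday rule) | 4 | 12 |
| Thursday | Monday, day 5 (Sunday rule) | 4 | 60 |
| Friday | Monday, day 4 (no rule applies) | 2 | 60 |

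**Half-life.** None is stated, so it has to be inferred. Table 2 (section 2.2.3.2) gives AUC(0-12h) as "1.55 1.05 ± 0.42 1.87 ± 0.49 0.99 ± 0.37" µg·hr/mL and steady-state Cmax as 379, 222, 348 and 171 ng/mL, with n = 1, 6, 3 and 3. The ratios are 1.55/0.379 = 4.09 h, 1.05/0.222 = 4.73 h, 1.87/0.348 = 5.37 h and 0.99/0.171 = 5.79 h. For a one-compartment bolus at steady state, AUC/Cmax = (1 − e^(−12k))/k. Solving for k gives half-lives of 3.03, 3.65, 4.38 and 4.92 h, so I use 3-5 h.

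**Monday pre-dose level.** Let q = 2^(−12/t½), the fraction left after 12 hours. The steady-state trough is q/(1 − q) in units of one dose's peak. With n doses 12 hours apart, the last one 60 hours before, the level is q⁵(1 − qⁿ)/(1 − q). The ratio to the trough is therefore q⁴(1 − qⁿ), with n = 4 for a Thursday start and n = 2 for a Friday start.

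- t½ = 3 h: q = 0.0625, ratio 0.0015%.
- t½ = 4 h: q = 0.125, ratio 0.024%.
- t½ = 5 h: q = 0.189, ratio 0.13% (Thursday), 0.12% (Friday).
- t½ = 12 h, as a stress case: q = 0.5, ratio 5.9% (Thursday), 4.7% (Friday).

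**Monday 2-hour level.** The shortfall against the steady-state 2-hour level is q − q⁵(1 − qⁿ), which is almost exactly q: 6.2%, 12.5% and 18.9% at 3, 4 and 5 h.

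**Check with oral absorption.** A bolus exaggerates the 2-hour effect for an oral drug. I refitted Table 2 to a one-compartment model with first-order absorption at assumed rates of 1, 2 and 3 per hour. The half-lives become 1.45-2.65, 2.0-3.4 and 2.25-3.8 h, and the 2-hour shortfalls 0.5-5.5%, 1.6-9% and 2.5-11%. The pre-dose level remains below 0.02% of the trough throughout.

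**Unaffected starts.** With n doses at 12-hour spacing and no gap, the pre-dose level is 1 − qⁿ of the trough. A Wednesday starter sampled on day 3 (n = 4) reaches 99.87% or more at 3-5 h; Monday and Tuesday starters (n = 6) are higher still.

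**The case against.** The strongest reply is that no planned analysis is harmed. Section 13.2.3 plans compartmental estimates and NONMEM. It names no trough summary, accumulation ratio or day 1 versus day 4 comparison. Section 9.1.1.2 requires exact times ("Sites are to record the exact time that the sample is drawn along with the exact time that the study drug is administered"), and the diary in section 5.1 records each dose with its date and time. A model given that history handles the weekend correctly. Section 8.1 also describes linear PK, so steady state can be predicted from the day 1 profile. All of this stands, and it limits the harm to the label and to any observed-trough use. It does not recover a trough that was never observed: a prediction from day 1 assumes the behaviour that the steady-state visit could check.

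The 2-hour effect is small against the between-patient variability in Table 2, where SD/mean for Cmax is 39/171 = 23%, 55/348 = 16% and 64/222 = 29%. That also stands; the trough is the substance of the point.

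Sedated children are a real exception. If they took a dose on the Sunday night, as the night-before instruction might suggest, a sample 12 hours later would be 1 − q = 81-94% of the trough at 3-5 h. That reading conflicts with the Monday-to-Friday schedule, and the documents do not settle it or say how many children it concerns.

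Finally, section 13.1.1 escalates on DLT counts, so dose finding is untouched, and the protocol abstract names toxicity and safety as the Phase I primary endpoints. Both are correct. PK during radiation is nevertheless listed as a Phase I primary objective, and its sampling is required.

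**Conclusion.** The concern holds. For Thursday and Friday starters on the standard schedule, the sample labelled as a steady-state pre-dose level is taken about 60 hours after the last dose and is essentially zero: 0.0015-0.13% of the trough at a half-life of 3-5 h. The half-life is inferred from ratios of group means in very small groups, but the conclusion does not depend on it, since even 12 h gives only 5-6%. The 2-hour sample is modestly low, by about 0.5-19% depending on the absorption model.

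The number of patients affected cannot be derived from the documents. It would be 2/5 = 40% if start days were spread evenly over the five weekdays, which is an assumption. Section 13.3 expects 12-18 Phase I patients, so even a few lost troughs matter. The point is worth correcting but does not threaten dose escalation or the model-based PK analysis.

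**What to change.** In section 9.1.1, keep day 4, and day 3 when day 4 is a Saturday. Replace the Sunday rule with one for Thursday and Friday starters: take the steady-state samples on the Wednesday of the following week, which is day 7 or day 6. That is the third consecutive dosing day, with four doses since the gap, so the pre-dose level is 1 − q⁴, or at least 99.87% of the trough at 3-5 h. It stays within the first seven days. Word the rule as the third consecutive dosing day, normally Wednesday, because section 5.1.1.1 anticipates holiday delays. After a Monday holiday this becomes Thursday, which is day 8 for a Thursday starter, so the reference to the first week would need to allow for it.

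Make matching edits where day 4 appears in the abstract, 9.1.1.1 and 9.1.1.3. The passages on night-time dosing for sedated children and the Monday-to-Friday schedule must be reconciled, so that the dosing history before a Monday sample is unambiguous.

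Monday samples already taken should be flagged, left out of any steady-state summary, and entered in the PK model with their actual dosing history.

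The cost is small edits in four places. There are no extra samples or blood, and the draw moves from Monday to Wednesday for these patients.
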